**Analysis of Aim 1:** To compare the training programs on Interventionist uptake. We will conduct pre and post surveys to assess changes in knowledge and assess satisfaction with the training. COPE interventionists will need to demonstrate Knowledge and Competency in treatment delivery to be certified by PIs and [name] in COPE delivery, a measurement approach we use effectively in our trials (56). We will conduct a noninferiority analysis to determine if online training compared to high intensity face-to-face training results in same or better in Knowledge and Competency scores. Independent-samples t test, 2 test, and Fisher's exact test will be used to compare the groups.

**Analysis of Aim 2:** The fidelity model will be used to compare sessions delivered by interventionists under the two different conditions (online versus traditional face-to-face training conditions). The accuracy of the computationally derived "best model" automatic summarization fidelity ratings ("excellent", "acceptable", "problematic") will be evaluated against human ratings for all recorded sessions (N=600). The comparison of the automated fidelity relative to human fidelity rating will be evaluated through a comparison of agreement (Kappa coefficient). Human ratings will

be conducted by Ors [name] and [name] using the COPE Adherence Scale (1= excellent, .5 = acceptable, 0=problematic).

**PHASE 3 - Efficacy of COPE on PACE participant outcomes by type of COPE training:** This aim will be accomplished by evaluating dyad outcomes of the COPE program under the two different training approaches. Following training, each of the PACE organizations will enroll 5 persons with dementia and their caregivers in the study. This will yield 50 family dyads (25 dyads in traditional training sites and 25 dyads in online training sites). At 4 months, all dyad study outcomes will be assessed (Table 2).

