serve as the control site in which training will be provided via the virtual/remote training lead by a trained OT; 5 PACE organizations will serve as the comparison and be trained through the online training site. Prior to randomization, we will carefully examine PACE organizations on important variables such as size, location (urban; rural) percent of persons with dementia, and staff: participant ratio. In each site, one occupational therapist (OT) and one nurse (RN) will be trained (e.g., 5 OTs and 5 RNs in virtual/remote training sites; 5 OTs and 5 RNs in online training sites for a total of 10 OTs and 10 RNs or 20 health providers) Re-randomization procedures. Because COPE will be delivered by PACE staff to multiple participants with dementia within each organization, randomization at the individual participant level could lead to significant contamination between treatment and control conditions within an organization. Prior to randomization, we will collect organization-level data and have measures of organization size (or capacity), location (urban, suburban, rural), and summary characteristics of the participant population at each organization (e.g., percentage with dementia diagnosis, percentage minority). Because we will randomize ten organizations to five virtual/remote and five online training organizations, notable and problematic imbalances on at least a few organization-level characteristics could easily occur by chance in a single randomization. Methodological innovations are needed to achieve balance on these multiple organization-level characteristics while still maintaining the experimental rigor and inferential value of true random assignment. [name] will implement a re-randomization approach to achieve these important methodological goals. The balance match weighted (BMW) design is an innovative re-randomization procedure that is particularly well suited to our goals (54). Using the BMW approach, we will: 1) finalize the list of important covariates for which we desire matching or balancing across intervention and control organizations, 2) generate 20 lists of random assignments for these 10 organizations into intervention and control conditions, 3) calculate propensity scores of intervention assignment as a function of the covariates, and 4) select the random assignment list that minimizes the propensity score differences between intervention and control organizations. The BMW approach provides a random assignment distribution that has an optimal balance on multiple organization-level characteristics. This will result in even greater control over potential covariate influences and provide somewhat greater power to detect a COPE program effect. Treatment Conditions: COPE Online Training: Trinity PACE Organizations assigned to the COPE Online Training will receive the 10- Module training program described above. Designated OT/ RNs at the assigned PACE Organization will be emailed unique log-in details and instructions for completing the online training within the 3-day training window (to align with control group training) but at their own pace. Log-in details including date, time and duration in training sessions will be tracked. COPE Virtual/Remote Training: We will train one OT and one RN at each of the five PACE organizations randomly assigned to the virtual/remote training. [name] will conduct trainings. Our training program will involve up to 3 days which include about 4 hours of initial readings, PowerPoint presentations, and case presentations. Training will take place via web conference (via GoToMeeting.com or other platform) sessions. We will offer three of these training sessions to accommodate COPE staff members' schedules and assure an interactive process. Further, interventionists will participate initially in monthly tele-conference or web conference sessions and then 6 times a year over the duration of intervention delivery. Sessions will involve case presentations, troubleshooting, and adherence monitoring. We have used this approach in multi-organization endeavors with up to 15 interventionists actively participating by telephone. Using a structured agenda and assigning case presentations a priori facilitates productive discussions. We have allocated funds for COPE staff members time to participate in training and follow-up bimonthly calls to troubleshoot cases. Both groups will participate in monthly debriefing sessions which will be recorded and used to understand type of questions asked, problems encountered etc., to compare the two training groups. We have a specific agenda and methodology for interventionists to provide case reports (55). We will also establish a password secure and encrypted email list serve for interventionists to post challenges and receive feedback from PIs and other interventionists.

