
**PHASE 3 (Aim 3): Efficacy of COPE on PACE participant outcomes by type of COPE training.**  
This aim will be accomplished by evaluating dyad outcomes of the COPE program under the two different training approaches. Following training, each of the PACE organizations will enroll 5 persons with dementia and their caregivers in the study. This will yield 50 family dyads (25 dyads in traditional training sites and 25 dyads in online training sites). At 4 months, all dyad study outcomes will be assessed

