**Analysis of Aim 3:** To compare the efficacy of COPE on participant outcomes. One-sided to-sample t-tests will be used to examine non-inferiority at 4-months. Upper and lower 95% confidence intervals will be presented for means and medians. Assumptions of normality and equality of variance between groups will be evaluated using Shapiro-Wilk and modified Levene's tests, respectively. Should the variances be unequal, the Aspin-Welch unequal variance t-test will be used to examine non-inferiority; should the normality assumption be violated, the non-parametric Mann-Whitney U test will be used to examine non-inferiority. Descriptive statistics including measures of central tendency (mean, median, mode) and variation (standard deviation, interquartile range, range) for continuous measures as well as frequencies and percentages for dichotomous and categorical variables will be run for all measures at each timepoint. Outliers will be assessed by visual inspection of distributions and checked for accuracy. Histograms and Q-Q plots will be used to evaluate assumptions visually. Two-sample t-tests (or non-parametric Wilcoxon tests, as necessary) and Fisher's exact tests will be used to examine differences in demographic and treatment variables between intervention groups at each timepoint. To demonstrate that the online COPE training intervention is the same or better than the virtual/remote training intervention with regards to participant outcomes, one-sided two-sample t-tests will be used to examine non-inferiority at 4 months. Upper and lower 95% confidence intervals will be presented for means and medians. Assumptions of normality and equality of variance between groups will be evaluated using Shapiro-Wilk and modified Levene's tests, respectively. Should the variances be unequal, the Aspin-Welch unequal variance t-test will be used to examine non-inferiority; should the normality assumption be violated, the non-parametric Mann-Whitney U test will be used to examine non-inferiority.

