to be provided to the DSMC for this proposed trial. Primary responsibilities: The DSMC will be responsible for reviewing the safety of study participants during the conduct of this study and provide recommendations to the research team on specific aspects of the research protocol as it pertains to safety, potential study alerts and adverse events. Specific responsibilities of the DSMC will be to: a) provide an independent periodic review of recruitment and enrollment progress; b) review adverse events (AEs) including serious events and offer recommendations regarding the trial based on such observed events; c) serve in a consultative capacity to the research team regarding study procedures to address ethical dilemmas (e.g., reporting of abuse), safety of subjects in the trial, and appropriateness of all study procedures. Composition of the DSMC: The DSMC will be an independent multi-disciplinary group consisting of biostatistical, applied research and clinical experts who collectively have experience in practical trial designs, multi-site trials and mixed methods. The 3 to 5 member board will have no apparent conflict of interest with the investigative team or study including financial, scientific or regulatory in nature. DSMC members will be responsible for advising the PIs of any changes in their relationship and/or financial interests that occur during the course of the trial. The DSMC and PIs will be responsible for deciding whether these changes create a conflict of interest. Any DSMC member who develops a conflict of interest during the course of the trial will be asked to resign from the DSMC and another person with similar areas of expertise will be sought. Otherwise, DSMC membership is to be for the duration of the trial. DSMC Meetings, Documentation: We propose that the DSMC have one face-to-face meeting prior to entering into the field for the trial and one teleconference call each subsequent year unless the DSMC decides and votes otherwise at its first organizational meeting. More frequent meetings or teleconferences may be held in the rare need to review serious adverse events from the trial at the discretion of the DSMC. At the initial meeting in year 01 (anticipated to occur in month 5 prior to entry into the field), the DSMC will review all study procedures including data collection forms, intervention protocol and oversight plan. At this meeting, the DSMC will agree on whether there should be interim analyses, and if so, the stopping rules and interim analysis plan that avoids potentially biasing the investigative team. Modifications to protocols based on the DSMC review will be made prior to entering the field. At subsequent conference calls, the DSMC will review the progress of the study (accrual rate, protocol deviations and interim study analyses if recommended) and make recommendations. A representative of the research team will keep minutes of these meetings. A copy of the minutes approved by the DSMC will be shared with the IRB of UPENN. The minutes will include recommendations of the DSMC and be provided to the NIH after each meeting. Meetings of the DSMC will be open unless the DSMC requests otherwise. A closed meeting of the DSMC may be requested if it is deemed necessary to review outcomes data. The DSMC chair or their designate will take meeting notes of closed sessions. Provision of Data for DSMC Review. Interim Analyses: We elect not to consider interim analyses in this study due to the extended time for recruitment and the low likelihood of a sufficiently large effect that would make it possible to stop early. This study is designed as a non-inferiority trial in which two different training methodologies are being evaluated. Outcomes of the COPE program for people with dementia and caregivers are secondary and serve to confirm (or not) whether the online training approach is as good or better than traditional face-to-face intensive training. However, we will revisit this decision with the DSMC at its first organizational meeting. Adverse Event (AE) Reporting: The DSMC will be notified by the PI of any serious AE within 48 hours of initial notification to the project team that is attributed to the intervention (low or high probability). All members of the DSMC will receive copies of all safety reports at the time of their submission to the IRB. Safety Monitoring Plan: We do not anticipate any adverse reactions to the training approaches or implementation of the COPE program. Based on our previous work and studies in this area by others, there is only a small risk that family caregivers or persons with dementia will become increasingly anxious to the point that it becomes an adverse event (e.g., harmful to self or others) as a consequence of the COPE program. However, interviewers/ interventionists will be well trained to manage this reaction or make an effective referral if necessary and documentation of all such events will occur. Recruitment and AE Reports: Reports presented to the DSMC will include data on enrollment (study accrual by month; comparison of expected to actual enrollment; number of individuals screened, number eligible and number ineligible, number randomized by gender, and AEs. Also, the DSMC will receive reports of the number of study participants who discontinue from each study arm (those receiving COPE from interventionists trained via face-to-face/virtual versus those receiving COPE from interventionists trained via online program) and/or the study and reasons for discontinuation. We propose that reports be provided to the DSMC twice yearly. However, the DSMC will decide upon the schedule of

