Demographics (age, gender, race, ethnicity, education and years employed by Trinity) will be collected at baseline for all trainees as well. At baseline, one representative from each site will complete a baseline questionnaire about their site's staff-participant ratio and location characteristics (urban rural, suburban). At baseline, study team members will collect demographics (age, gender, race, ethnicity, education, address, age, living arrangement, employment status, neighborhood characteristics, relationship status and duration of care) of caregivers and persons with dementia and self-reported data on incomes and feelings of financial strain. The following study instruments will be administered to all caregivers at baseline and four months. The Caregiver Relationship Scale will assess the relationship of person with dementia and their caregiver. The LSNS-R: Caregiver Social Support measure will gather self-reported data about the quality of support received from family and friends. The health-related quality of life and functional ability of the person with dementia will be collected using the Short-Form 36 (SF-36). Caregivers will report the dependence level and functional ability of the person with dementia via the CAFU. Caregivers will report on the presence of a set of behaviors exhibited by the person with dementia, the severity and frequency of those behaviors and level of distress felt by the caregiver via an adapted version of the NPI-Q (Neuropsychiatric Inventory). Caregivers will self-report the sense of capability and confidence in providing support to person with dementia via the Short Sense of Competence Questionnaire (SSCQ): 7 items. Caregivers will self-report feelings of depression via the PHQ-9. Caregivers will self-report their perceptions of caregiving skills via the Caregiver Mastery. Caregivers will self-report their perception of change in wellbeing via Perceived Change for Better Index (13 items). Caregivers will report the quality of life of the person with dementia via QOL-AD CG. Caregivers will self-report their confidence level taking care of PLWD via the CG Confidence in Using Activities and Caregiver Confidence in Medical Sign/Symptom Management. Caregivers will self-report perceived burden as a caregiver of person with dementia via Caregiver Burden. Caregivers intervention progress will be tracked and collected via an intervention instrument called the summary of problem areas and caregiver progress.

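### Aim 3 compares dyad outcomes at 4 months without the baseline scores already collected; adding each instrument's own baseline is a cheap precision gain of uncertain size, not the repair of an error.

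*Combined protocol and SAP*

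**What the plan says.** The Analysis of Aim 3 paragraph (Analysis Plan) states the test twice: "One-sided to-sample t-tests will be used to examine non-inferiority at 4-months" and, further on, "one-sided two-sample t-tests will be used to examine non-inferiority at 4 months". Aspin-Welch replaces the t-test if variances differ, and Mann-Whitney replaces it if normality fails. On reporting it says "Upper and lower 95% confidence intervals will be presented for means and medians". Neither statement names a covariate, and the visible text contains no analysis of covariance, change score or repeated-measures model for Aim 3. The tests planned at each timepoint compare demographic and treatment variables between groups; they do not adjust the outcome. The re-randomization procedure balances characteristics of organizations, not dyad scores.

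Study Instruments says "The following study instruments will be administered to all caregivers at baseline and four months", so a baseline score on the same instrument exists for the measures listed there.

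Three other statements bear on the size of the point. Ten organizations are randomized, five to each training method, and "In each site, one occupational therapist (OT) and one nurse (RN) will be trained". Under Phase 3, "Following training, each of the PACE organizations will enroll 5 persons with dementia and their caregivers in the study", giving 25 dyads per arm. Data and Safety Monitoring (Interim Analyses) calls the dyad outcomes secondary, with the role of confirming the training comparison.

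**The concern.** With 50 dyads the Aim 3 intervals will be wide, and the plan does not use a covariate it already pays to collect. A person's own baseline score is often the best single predictor of the later score. Using it removes explained variance from the comparison at the price of one degree of freedom.

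There is a second, smaller reason. Dyads are enrolled after their organization has been allocated and its staff trained, so the arms could differ at baseline through who is recruited as well as by chance. Adjustment gives partial protection against that; the planned test gives none.

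At stake is the precision of a secondary comparison. The validity of the planned test is not in question under chance imbalance.

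**Working it through.** **Inputs from the documents.** 10 organizations × 5 dyads = 50, or 25 per arm; 95% intervals; same-instrument scores at baseline and 4 months. The plan gives no Aim 3 power or precision figure, so there is none to reproduce.

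**Inputs assumed.** Outcome SD = 1; r = 0.3, 0.5, 0.7 (and 0 as a check); ICC = 0.10 for clustering; no missing data.

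**Step 1. Planned comparison, dyads treated as independent.**
Half-width = t(0.975; 48) × √(2/25) = 2.0106 × 0.2828 = 0.569 SD.

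**Step 2. Same comparison with baseline as covariate.**
Half-width = t(0.975; 47) × √[(2/25)(1 − r²)(1 + 1/46)], with t = 2.0117. The factor 1 + 1/46 is the expected cost of chance baseline imbalance.

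| r | Half-width (SD) | Change from 0.569 |
|---|---|---|
| 0 | 0.575 | 1.1% wider |
| 0.3 | 0.549 | 4% narrower |
| 0.5 | 0.498 | 12% narrower |
| 0.7 | 0.411 | 28% narrower |

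Steps 1 and 2 are equal at r = 0.1495. That is an average. In 40,000 simulated trials per value of r, the adjusted interval was the narrower one in 40% of trials at r = 0.15, 52% at 0.2, 76% at 0.3 and 98% at 0.5.

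**Step 3. Inference at organization level.** Five dyads per organization give a variance factor of 1 + 4 × ICC = 1.4 at ICC 0.10. The unadjusted half-width on 8 df is 2.306 × √(2 × 1.4/25) = 0.772 SD. The gain from a dyad-level covariate depends on how well baseline predicts the organization component. One therapist and one nurse per site deliver COPE, so part of that component may arise after baseline. Three cases, as the ratio of adjusted to unadjusted standard error:

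- (a) Baseline predicts both components equally: √(1 − r²).
- (b) Baseline predicts none of the organization component: √{[0.5 + 0.9(1 − r²)]/1.4}.
- (c) Baseline has its own organization component, unrelated to the outcome's: √{[0.5(1 + r²) + 0.9(1 − r²)]/1.4}.

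| Case | r = 0.3 | r = 0.5 | r = 0.7 |
|---|---|---|---|
| (a) | 0.954 | 0.866 | 0.714 |
| (b) | 0.971 | 0.916 | 0.828 |
| (c) | 0.987 | 0.964 | 0.927 |

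These formulas leave out the cost of estimating the slope, about 1% at r = 0 in simulation. With that cost included, case (c) simulates at about 1.00, 0.96 and 0.93. The reductions are therefore about 5%, 13% and 29% in (a), 3%, 8% and 17% in (b), and 0%, 4% and 7% in (c).

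**Step 4. Two alternatives that do worse.**
- Covariate entered as a site mean: 8 df become 7, and the half-width is multiplied by (2.3646/2.306) × √[(1 − r²)(7/6)], with r now the correlation between site means. This equals 1 only at r = 0.43.
- Simple change score, dyads independent: 2.0106 × √[4(1 − r)/25] = 0.673, 0.569 and 0.441 SD at r = 0.3, 0.5 and 0.7. This is worse than Step 2 throughout and worse than the planned test below r = 0.5.

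**The case against.** The strongest case for leaving the plan alone has four parts.

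- **The test is valid and the outcomes are secondary.** This stands, and it is why the point is an efficiency suggestion. A reader might infer that the unadjusted comparison is biased or that the plan is in error. The documents do not support that: with organizations randomized, chance imbalance at baseline does not bias the comparison. Enrolment after allocation makes a recruitment difference possible, but nothing shows that one occurred.
- **The 0.15 threshold is fragile.** This also stands. A reader might infer that any correlation above 0.15 guarantees a narrower interval. It does so only on average, for 50 independent dyads, whereas the trial randomizes 10 organizations. In case (c) there is essentially no gain even at r = 0.3.
- **No margin is visible.** A narrower interval cannot by itself deliver a non-inferiority conclusion, and adjustment does not supply the margin. The precision gain remains, but its effect on the verdict cannot be stated.
- **Scope is uncertain.** The Phase 3 text refers to a Table 2 that is not in the visible text, so the endpoint list is unknown. Caregiver wellbeing is one of the Aim 3 domains, and the instrument described in those terms, the Perceived Change for Better Index, asks about change itself. A baseline covariate has little meaning there, so the fix may not reach that domain.

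These limits shrink the benefit but do not remove it: nothing visible already uses the baseline scores, and the loss if they prove useless is about 1%.

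**Conclusion.** The point holds as a modest, low-cost improvement. The two Aim 3 statements specify unadjusted tests at 4 months, and the same-instrument baseline is collected but unused. Ignoring clustering, the expected gain is 4% to 28% of interval width for r from 0.3 to 0.7. With organization-level inference at ICC 0.10 it runs from about nil to 29%, depending on r and on how baseline relates to the organization effect. At r = 0.3 the gain is small in every case.

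All of this rests on assumed r and ICC, complete data and 25 dyads per arm. It would be wrong to read the adjustment as making the non-inferiority analysis complete. Accounting for the 10 organizations is a separate matter that widens the unadjusted interval (0.569 to 0.772 SD at ICC 0.10). Of the adjusted cases in Step 3, only the most favourable (0.714 × 0.772 = 0.551 SD) comes back below 0.569.

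**What to change.** Before between-arm outcomes are examined, amend the Analysis of Aim 3 as follows.

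1. Make the main analysis the 4-month score on training arm plus the same instrument's dyad-level baseline score. Fit it in whatever model accounts for the 10 randomized organizations, and do not enter baseline as a site mean.
2. Read non-inferiority from the adjusted difference and its confidence interval, and state the one-sided level that matches (2.5% for a two-sided 95% interval).
3. Omit the baseline covariate for instruments that ask about change, such as the Perceived Change for Better Index.
4. Do not substitute a simple change score.
5. Name a fallback for non-normality that keeps the covariate, for example an organization-level permutation test of the adjusted difference that follows the re-randomization rule.
6. Keep the planned t, Welch and Mann-Whitney tests as sensitivity analyses.

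The cost is SAP wording and one covariate per outcome, with no new data. The statistical price is about 1% in width if baseline proves uninformative. The organization-level model and the margin are needed in any case and are not part of this cost. The protocol is dated January 2025, and the Consent Process section refers to participants already active in September 2022. If outcomes by arm have already been seen, report the adjusted analysis as supplementary and say when it was specified.

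### Aim 3: a normality pre-test can replace the t-test for non-inferiority with Mann-Whitney, so the data choose the quantity tested, and no interval for the arm difference is clearly planned

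*Combined protocol and SAP*

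**What the plan says.** The Analysis Plan (Analysis of Aim 3) gives the same procedure twice in one paragraph.

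- Starting test: "one-sided two-sample t-tests will be used to examine non-inferiority at 4 months".
- Pre-tests: "Assumptions of normality and equality of variance between groups will be evaluated using Shapiro-Wilk and modified Levene's tests, respectively".
- Variance branch: "Should the variances be unequal, the Aspin-Welch unequal variance t-test will be used to examine non-inferiority".
- Normality branch: "should the normality assumption be violated, the non-parametric Mann-Whitney U test will be used to examine non-inferiority".
- Intervals: "Upper and lower 95% confidence intervals will be presented for means and medians".

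On size, the Phase 3 (Aim 3) section says that "each of the PACE organizations will enroll 5 persons with dementia and their caregivers in the study", and that "This will yield 50 family dyads (25 dyads in traditional training sites and 25 dyads in online training sites").

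The text available for review does not state:

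- a non-inferiority margin, the one-sided level, or an SD or power for Aim 3;
- the level of the pre-tests, or whether Shapiro-Wilk is applied per arm or to residuals;
- which branch wins if both pre-tests fail;
- how a margin enters the Mann-Whitney test.

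The Data and Safety Monitoring section calls the dyad outcomes secondary and confirmatory of the training comparison.

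**The concern.** A non-inferiority claim needs one quantity, one margin and one error rate, all fixed in advance. Here the observed distribution decides which quantity is tested. The pooled t-test and Welch address the difference in means. Mann-Whitney addresses whether a dyad from one arm tends to rank above a dyad from the other. The two agree when one arm is a shifted copy of the other, and part company when the arms differ in shape.

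The direction matters. If online training works for most dyads but fails badly for a few, the mean falls, while the ranks record only that those few are at the bottom, not how far down. A trial of whether a cheaper training route is good enough should be able to see that failure. The same rule can also err the other way, and two outcomes under the same aim could be judged on different quantities.

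Two further gaps sit beside this. A margin for the arm difference cannot be read against intervals for each arm's mean or median. And a one-sided test at an unstated level is paired with 95% intervals, so test and interval can disagree: a two-sided 95% interval corresponds to one-sided 2.5%, not 5%.

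**Working it through.** **The plan's own figure.** 10 organizations × 5 dyads = 50; 5 organizations × 5 = 25 per arm. This reproduces, but only as a count, because no margin, level or power is attached to it.

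**What follows from the text alone.** If Mann-Whitney is run on unshifted scores, it tests for a difference or superiority, not non-inferiority. If the margin is first added to the online scores, it tests a mean difference only under a pure shift. The simulations use the second version, which is the more generous to the plan.

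**Inputs.**
- From the documents: 25 per arm and the switching rule.
- Assumed: control SD 1; margin 0.3 to 0.7 SD; both pre-tests at 0.05; Shapiro-Wilk per arm, taking precedence over median-centred Levene; independent dyads.
- True mean deficit set equal to the margin, so every declaration of non-inferiority is false.
- Subset scenarios: a share of the online arm carries the whole deficit, shift = margin/share. For a 0.7 SD margin: 0.7/0.25 = 2.8 SD, 0.7/0.20 = 3.5 SD, 0.7/0.10 = 7.0 SD.

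With 4,000 runs, the simulation standard error is √(0.05 × 0.95/4000) = 0.3 points at a 5% rate and √(0.15 × 0.85/4000) = 0.6 points at 15%.

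**False non-inferiority at one-sided 5%.**

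| Scenario | Planned route | Welch always |
|---|---|---|
| Both arms normal | 5.2% | 5.1% |
| Skewed (exponential), pure shift, two runs | 4.8%, 6.0% | 5.1% (first run) |
| 30% subset, margin 0.3 to 0.7 SD | 4.7 to 6.8% | 4.4 to 5.7% |
| 25% subset, margin 0.3 to 0.7 SD | 5.2 to 8.5% | 5.1 to 5.4% |
| 20% subset, margin 0.5 SD | 7.9% | 5.9% |
| 20% subset, margin 0.7 SD, three runs | 14.6 to 15.3% | 5.3 to 6.5% |
| 15% subset, margin 0.5 SD | 13.0% | 7.0% |
| 10% subset, margin 0.5 SD | 22.7% | 7.2% |
| 10% subset, margin 0.7 SD | 42.8% | 9.8% |
| Strong skew to the bad side, online SD 1.2 times larger, margin 0.7 SD | 12.4% | 5.6% |
| Same, online SD 1.5 times larger | about 21% | about 7% |
| Strong skew to the good side, online SD 1.5 times larger | 0.7 to 1.0% | 3.2 to 3.9% |

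At one-sided 2.5% the pattern is the same (planned route against Welch): normal 2.7% against 2.6%; 20% subset at 0.7 SD, 9.2% against 3.6%; 10% subset at 0.7 SD, 31.2% against 7.0%.

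**Which branch is responsible.** In the 10% subset, 0.7 SD case, Mann-Whitney used alone gives 42.7%, against 42.8% for the full rule. The pooled t-test and Welch differ by at most about 0.2 points at 25 against 25. Applying Shapiro-Wilk to residuals instead of per arm changes the subset results by less than 1 point.

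**A case tied to the design.** Each organization supplies 5 of the 25 dyads in its arm, which is 20%. If exactly five online dyads carry the whole 0.7 SD deficit, the planned route gives 8.5% and Welch 1.1%.

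**Precision of the proposed interval.** Half-width = t × √(2/25) = t × 0.283 SD. One-sided 5%: 1.677 × 0.283 = 0.47 SD. Two-sided 95%: 2.011 × 0.283 = 0.57 SD.

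**The case against.** The strongest objection is that no error rate can be derived from these documents. Without a stated margin and level, none is defined, and every figure above 6% needs an assumed subset share and depth, or an assumed skew and SD ratio. This stands. The larger figures need a few dyads 3 or more control-arm SDs below the rest. With a 15% subset and a total deficit of 0.7 SD, an extra subset deficit of only 1 to 2.5 SD (the remainder spread over the whole arm) gives 4.6 to 6.9%. Bounded questionnaires may leave no room for deeper falls, and milder skew gives smaller rates.

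A reader might infer that the plan has a false-positive rate of 15 to 20%. The documents do not support that: it is neither derivable nor a ceiling, and many plausible settings stay near nominal. A reader might also blame the variance step or the interval wording for the inflation. Neither causes it. The Levene/Welch branch adds almost nothing with equal arms, and intervals do not alter a test's error rate. The interval wording is also ambiguous: it does not say per arm, although that is the natural reading.

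Two further points stand. The simulation treats dyads as independent, whereas they are grouped five to an organization; clustering is a separate issue that Welch does not address. And Welch is not exact under heavy tails at this size.

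What survives is that the rule lets the data choose the quantity tested, and that the branch chosen under non-normality is weakest against a failure confined to a small part of the online arm.

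**Conclusion.** The point holds as a defect of specification in a secondary analysis. Followed as written, the Aim 3 rule can test a mean difference for one outcome and a rank comparison for another, with no stated way to apply a margin to the second and no interval clearly planned for the arm difference.

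Its effect on false non-inferiority depends on shape. On the assumptions listed (25 independent dyads per arm, margin 0.3 to 0.7 SD, one-sided 5%, margin added before Mann-Whitney):

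- normal data or a pure shift: about 5 to 6%;
- poor-responder subsets of 25% or more: at most about 8.5%;
- smaller, deeper subsets, or strong skew to the bad side with a larger online SD: about 12 to 21% in the intermediate cases and up to about 43% in the most extreme;
- tail on the good side: about 1%, so the rule is then too strict.

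Welch was closer to nominal in every clearly inflated case, though it reached about 10% at worst. The trial's main comparison of training methods is not touched by this point.

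**What to change.** For every Aim 3 outcome that is to be tested for non-inferiority:

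1. Name the online-minus-control difference in means at 4 months as the quantity of interest, and state the margin and the direction of benefit for each scale.
2. Estimate it by one pre-specified method without pre-tests: Welch, or the organization-level or cluster model if one is adopted.
3. Declare non-inferiority only if the two-sided 95% confidence interval for that difference excludes the margin, which is one-sided 2.5%.
4. Report that interval for each outcome. Intervals for each arm's mean and median can remain as description.
5. Keep Mann-Whitney and a bootstrap interval for the mean difference as sensitivity analyses only. Histograms and Q-Q plots can stay as description, but should not select the test.

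The cost is SAP wording. If one-sided 5% was intended, the half-width at 25 per arm grows from about 0.47 to 0.57 SD, and the margin that can be shown with 80% power under no true difference grows from (1.645 + 0.842) × 0.283 = 0.70 SD to (1.960 + 0.842) × 0.283 = 0.79 SD. If the team prefers one-sided 5%, it should say so and use the two-sided 90% interval, so that test and interval agree.
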